## 2 SYNOPSIS

Study Title: A Prospective Observational Registry Study to Characterise Normal Conditions of Use, Dosing and Safety Following Administration of Vernakalant IV			
Condition/Disease: Atrial fibrillation			
Number of Patients	2000	Duration of Patient Participation	24 hours
Number of Sites (approx.)	45	Duration of Study	3 rd Quarter, 2011 – 1 st Quarter 2018 (approx.)

Rationale: Vernakalant IV, an atrial-selective ion channel blocker, has a differing mechanism of action that mitigates some of the main safety concerns of other anti-arrhythmic treatments. Vernakalant IV (BrinavessTM) has been recently approved by the European Commission for rapid cardioversion of recent onset atrial fibrillation (<=3 days duration for post-cardiac surgery and <=7 days duration for non-surgical patients). In view of the recognised limitations of spontaneous reporting, the Sponsor will conduct a post-authorisation safety study (PASS) of vernakalant IV in order to collect information about normal conditions of use and appropriate dosing, and to quantify possible medically significant risks associated with the use of vernakalant IV in real-world clinical practice.
			

Study Design: Observational, prospective PASS (no study intervention or procedures) of patients administered vernakalant IV within a network of clinical sites across EU member countries. Countries currently included are Austria, Denmark, Germany, Spain, and Sweden. Finland, and other EU and non-EU countries may be included but selection is conditional on a number of factors, including, but not limited to, the actual date of product launch in each country and rate of market uptake of vernakalant IV.
			

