## Vernakalant IV Sterile Concentrate Prospective Safety Registry Study

Sponsor Protocol Identifier: 6621-049-00

3 August 2016

---

unique to this technique, including skin burns, complications of sedation and malfunctions of a pacemaker or internal defibrillator. [Ref. 5.4: 104]

The potential adverse events of both electrical and pharmacological cardioversion and the limited efficacy of pharmacological cardioversion have warranted the development of novel therapeutic options. [Ref. 5.4: 371, 441]

Vernakalant, a medicine that acts preferentially in the atria, has a novel and unique mechanism of action. Controlled clinical trials [Ref. 5.4: 441] of vernakalant IV have been conducted to define the efficacy and safety profile of vernakalant IV. Two phase III randomised trials demonstrated that the conversion rate of recent onset ( $\leq 7$  days) AF to sinus rhythm was significantly better for Vernakalant compared to placebo (51.1% versus 3.8%, respectively;  $p<0.0001$ ) with an open-label trial demonstrating a conversion rate of 50.9%. [Ref. 5.4: 442] Another phase III randomised trial of post-cardiac surgery patients (CAD and/or VHD) demonstrated that Vernakalant was significantly better compared to placebo in the conversion of recent onset ( $\leq 3$  days) AF to sinus rhythm (47% versus 14%, respectively;  $p<0.001$ ). [Ref. 5.4: 210] In patients who converted to sinus rhythm, the median time to conversion was 11-13 minutes in those studies.

Clinically significant adverse reactions occurred infrequently. Clinically significant adverse reactions observed in the clinical program and described in detail in the Summary of Product Characteristics (SmPC) included: hypotension, ventricular arrhythmia, atrial flutter and bradycardia. Incidence rates for these adverse reactions are presented below, using pooled data from the placebo-controlled phase 2 and phase 3 clinical trials (773 patients received vernakalant, 335 received placebo). Because vernakalant IV is rapidly cleared from the circulation, adverse events from the start of infusion through the first 2 hours after infusion are considered, as these occur during the period of peak vernakalant exposure.

Adverse Reaction	Vernakalant	Placebo	$\Delta$ (95%CI)
Hypotension	7.6%	5.1%	2.5 (-0.6, 5.6)
CHF subpopulation	16.1%	4.7%	11.4 (3.3, 19.4)
Clinically meaningful hypotension*	1.2%	0%	---
CHF subpopulation	2.9%	0%	---
Ventricular arrhythmia	3.9%	3.2%	0.8 (-1.6, 3.2)

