### **6.3 Study Enrolment**

#### **6.3.1 Site Enrolment and Country Selection**

The PASS will target clinical sites in multiple EU member countries to set up infrastructure for prospective data collection on vernakalant IV. Countries currently included are Austria, Denmark, Germany, Spain, and Sweden. Finland, and other EU and non-EU countries may be included but selection is conditional on a number of factors, including, but not limited to, the actual date of product launch in each country and rate of market uptake of vernakalant IV. In addition, country selection was based on the following considerations: (1) the desire for the study to reflect geographic variation of patients across the EU member countries; (2) the ability to capture expected variation in use of different treatment modalities and clinical settings for cardioversion of recent onset AF across EU member countries; and (3) the Sponsor's expectation that in several of these countries, vernakalant IV will be commercially available for use within the first 1-2 months following the expected Commission Decision on the CHMP marketing authorization approval (MAA). The latter consideration was adopted in order to ensure that the study will collect the most timely data on real-world use of vernakalant IV.

Site enrolment progress will be monitored closely following the marketing launch of vernakalant IV across Europe. Any substantial delays in a country with clinical sites will trigger a reevaluation of this country's appropriateness for inclusion in the PASS. Under such circumstances, the Sponsor will inform the CHMP of this development and will consider inclusion of additional countries if needed.

Clinical sites in each country reflecting both academic and community hospitals in which acute cardioversion is routinely performed (IV pharmacologic or electrical) will be targeted for participation in the study. Centres with adequate prescription, hospital encounter, discharge and diagnostic data will be targeted in order to obtain good quality data about administration and expected safety profile of vernakalant IV in the context of normal clinical usage. All efforts will

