**Vernakalant IV Sterile Concentrate Prospective Safety Registry Study**

Sponsor Protocol Identifier: 6621-049-00

3 August 2016

---

At the completion of the study, stratified analyses will be used to present the results. Full statistical methods and analyses will be described in the Statistical Analysis Plan (SAP).

Patients are consecutively enrolled into SPECTRUM based on when they present at the participating site. In order to minimize any potential selection bias at the patient level, retrospective data collection will be conducted to include all patients already treated with BrinavessTM but not enrolled in SPECTRUM, at existing and newly qualified sites, with available key data. Specifically, data will be included from all patients who;

1. Have received BrinavessTM since April 2013 but were not enrolled in SPECTRUM.
2. Have available in their hospital records the key data variables as stipulated in section 7.2.1.
3. Provide their informed consent or the site obtains a waiver from their IEC.

Both retrospectively and prospectively included patients have to fulfill the same inclusion and exclusion criteria. As neither group of patients are selected randomly, this approach is not expected to yield selection bias. In addition, results will be reported overall and stratified by method of enrollment. As those who refuse to consent to participate, will not have provided their consent to use their data it would not be possible to compare baseline characteristics of those who refuse vs those who participate. To ensure the overall sample is not dominated by any one site or country by the inclusion of retrospective data, any site or country who reaches their limit based on the inclusion of retrospective data will be closed and the resources used to open other sites/countries. Enrolment will be capped at 10% per site (200 patients) and 40% per country (800 patients). This cap includes collection of patient data both prospectively and retrospectively.

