4 GENERAL CONSIDERATIONS FOR ANALYSIS

4.1 Sample Size and Power Calculations

Patients may be enrolled in the study more than once in association with multiple administrations of vernakalant IV. The study targeted 2,000 patients, per administration of vernakalant IV, across participating EU countries. The target sample size was selected in order to have adequate statistical precision as expressed by a two-sided, 95% confidence limit around the expected incidence rate for each HOI for sample sizes of 500, 1,000 1,500, and 2,000 patients. The incidence of each HOI during the first 24 hours post-vernakalant IV administration among patients randomised to receive vernakalant IV in the pooled phase II/III clinical trial database (n=889, including the AVRO Study [3]) ranged from 0% to 0.22% for each HOI.

[figure not shown]
Table A shows the margins of error, defined as the distance from the expected proportion to the upper limit of the confidence interval (CI) as shown in the table, and confidence limits of the two-sided 95% confidence intervals with sample size of 500, 1,000, 1,500, and 2,000, respectively. For example, if the expected proportion of significant hypotension is 0.003 and the sample size is 1,500, the margin of error is 0.004, and the lower and upper bounds of the two-sided 95% confidence interval will be 0.001 and 0.007, respectively. The calculation of the confidence intervals was performed using the Clopper-Pearson exact method [3] and PASS software (2008, Kaysville, Utah).

Table A Margins of error and confidence limits of the two-sided 95% confidence intervals for one sample proportion with various sample sizes.

Since the confidence interval is not symmetric around the expected proportion of patients with events, the precision is the distance from the expected proportion to the upper limit of the confidence interval as shown in this table.

| Sample Size | N=500 | | N=1,000 | | N=1,500 | | N=2,000 | |
|----------------|-----------------|-----------------------|-----------------|-----------------------|-----------------|-----------------------|-----------------|-----------------------|
| Expected Prop. | Margin of Error | Lower and Upper Limit | Margin of Error | Lower and Upper Limit | Margin of Error | Lower and Upper Limit | Margin of Error | Lower and Upper Limit |
| 0.001 | 0.008 | 0.000, 0.009 | 0.005 | 0.000, 0.006 | 0.003 | 0.000, 0.004 | 0.003 | 0.000, 0.004 |

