5 STATISTICAL ANALYSIS

Categorical variables (e.g., gender) will be summarised by the number and percentage (%) of patients. For the pre-specified HOIs, both stratified (based on enrolment method, i.e. prospective or retrospective) and unstratified (i.e. overall) cumulative incidences will be reported, and corresponding 95% confidence intervals will be displayed for each such specific HOI. Unless otherwise specified, the 95% confidence intervals around the proportions will be calculated using exact methods described by Clopper and Pearson [3].

Continuous variables (e.g., age) will be summarised using descriptive statistics (number of non-missing values, mean, standard deviation, median, Q1 and Q3, minimum and maximum values).

Some continuous variables will be described using categorizations to provide additional detailed information regarding vernakalant IV administration. For instance, percentage of weight-based dosing recommendation may be described using the following categories: < 70%, 70% to < 85%,

85% to < 95%, 95% to 105%, > 105% to 110%, > 110% and the duration of infusion will be reported in categories such as: < 7 minutes, 7 minutes to < 9 minutes, 9 minutes to 11 minutes, >11 minutes to 13 minutes, > 13 minutes. The categorizations will be based on the empirical data and may be adjusted.

Key results will be presented overall and by patient enrolment method (i.e. prospective or retrospective). Any changes to the analysis over the course of the study will be described in Statistical Analysis Plan (SAP) addendums or amendments. Ad hoc analyses (by country, site, or other) will be performed as requested by the sponsor.

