5.10 Secondary Objective #4: Rate of Conversion to Sinus Rhythm

For patients in the analysis population set and the effectiveness analysis population set, the rate of successful conversion to sinus rhythm for at least one minute within 90 minutes from the start of first vernakalant IV administration (Secondary Objective 4) will be expressed as the proportion of patients with successful conversion, together with the associated 95% confidence interval. (**Table 15a**). The rate of successful conversion to sinus rhythm without time restriction will also be expressed as the proportion of patients with successful conversion, together with the associated 95% confidence interval. The time (in minutes) from start of vernakalant infusion to conversion to sinus rhythm among those patients who converted will be summarised using appropriate measures of dispersion and central tendency (means, medians, ranges, Q1-Q3 ranges, and standard deviations) (**Figure 3**). As defined in Section 4.3, a pre-specified secondary analysis of the effectiveness of vernakalant will be restricted to a subgroup of patients who receive vernakalant IV in accordance with the SmPC (i.e., adult indication, therapeutic indication for AF, duration of AD \leq 7 days for non-surgery patients and \leq 3 days for post-cardiac surgery patients, and no contraindications) (**Table 15b**). Rates of successful conversion will also be

tabulated for all patients by non-surgery and post-cardiac surgery indications, respectively (**Table 15c, 15d**).

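### The confidence interval for the conversion rate ignores site clustering, so it is too narrow as a statement about practice beyond the enrolled sites; by how much depends on a within-site correlation the documents do not give

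*SAP*

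**What the plan says.** SAP section 5 gives the general rule: "Unless otherwise specified, the 95% confidence intervals around the proportions will be calculated using exact methods described by Clopper and Pearson". SAP 5.4 repeats the exact method for the HOIs. For Secondary Objective 4, SAP 5.10 asks only that conversion be "expressed as the proportion of patients with successful conversion, together with the associated 95% confidence interval", and the footnotes to Table 15a define it as a simple ratio of counts. The section 5 default therefore applies to Tables 15a-d.

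The unit of analysis is the treatment episode. SAP 4.1 states: "The study targeted 2,000 patients, per administration of vernakalant IV, across participating EU countries". SAP 4.2 and 5.1.1 treat repeat episodes of the same patient as independent.

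Neither document mentions an ICC, a design effect, a robust or clustered variance, or a random site effect. The only adjustment or stratification planned for the estimates is by method of enrolment (Protocol 10.2, SAP 5).

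On the grouping of patients, the Protocol synopsis expects about 45 sites. Protocol 7.2 caps a site at 200 patients (10%) and a country at 800 (40%). Protocol 6.3.1 lists among its country-selection criteria "the ability to capture expected variation in use of different treatment modalities and clinical settings for cardioversion of recent onset AF", and ties this to differences between EU member countries.

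**The concern.** The Clopper-Pearson interval assumes independent observations with one common probability. Three features of the plan make that doubtful for conversion.

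- **Early use of other cardioversion changes the endpoint itself.** Under SAP 4.2, an episode with electrical cardioversion or an intravenous class I/III drug within 90 minutes leaves the effectiveness population. Under footnotes 3 and 4 of Table 15a, such an episode cannot count as a success but stays in the denominator. A site that habitually moves to a shock early lowers its own rate in those rows.
- **Selection differs.** The German annex admits only use in line with the SmPC and excludes patients with listed contraindications. The main protocol does neither. Protocol 7.2 also says that ways of finding retrospective patients will differ between sites.
- **Site sizes are uneven.** Protocol Appendix I projects 445 of the last 810 patients from five Finnish sites (89 each if equal) and 55 from eight German sites (about 7 each).

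The study exists to describe real-world use. An interval that leaves out between-site variation would claim more precision for that purpose than the design gives.

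**Working it through.** **1. The plan's own figures.** SAP 4.1 expresses precision as a "two-sided, 95% confidence limit around the expected incidence rate for each HOI". Its worked example has proportion 0.003, n = 1,500 and limits 0.001 and 0.007. Clopper-Pearson from beta quantiles with x = 4.5 gives 0.0009 and 0.0073, which agrees. All 44 cells of Table A reproduce the same way, so the planned precision assumes independent binomial data.

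**2. Inputs for conversion.**
- N = 2,000 episodes (SAP 4.1).
- Conversion 51%, from the 51.1% and 50.9% quoted for earlier trials in Protocol section 3.
- About 45 sites (Protocol synopsis), so the mean size is 2,000/45 = 44.4.
- ICC: not in the documents. Assumed range 0.005 to 0.05. At 51% conversion the implied standard deviation of true site rates is sqrt(ICC x 0.51 x 0.49): 3.5 points at 0.005, 5.0 at 0.01, 7.1 at 0.02 and 11.2 at 0.05.

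**3. Planned interval.** Clopper-Pearson for 1,020/2,000 is 48.8% to 53.2%, a half-width of 2.2 points. The simple normal formula, 1.96 x sqrt(0.51 x 0.49/2,000), gives 2.19 against 2.21 for the exact method. The exact method's conservatism is thus about 1% of the half-width. With 45 equal sites an ICC of about 0.0005 uses it up.

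**4. With site as the cluster.** Design effect DE = 1 + (m_w - 1) x ICC, where m_w = sum(m²)/sum(m). Effective sample size = 2,000/DE, with Clopper-Pearson applied at that size. Approximate coverage of the unadjusted interval = 2Φ(1.96/√DE) - 1.

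Equal sites, m_w = 44.4:

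| ICC (assumed) | DE | Effective N | Half-width (points) | Coverage of planned CI |
|---|---|---|---|---|
| 0.005 | 1.22 | 1,643 | 2.5 | 92% |
| 0.01 | 1.43 | 1,394 | 2.7 | 90% |
| 0.02 | 1.87 | 1,070 | 3.0 | 85% |
| 0.05 | 3.17 | 630 | 4.0 | 73% |

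**5. Unequal sites, for illustration.** Suppose four of the 45 sites reach the cap of 200 and the other 41 share 1,200 equally (an assumption). Then m_w = (4 x 200² + 1,200²/41)/2,000 = 97.6. At ICC 0.01 and 0.05, DE is 1.97 and 5.83, the half-width 3.1 and 5.4 points, and coverage about 84% and 58%.

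**6. The retrospective column of Table 15a.** Appendix I projects 345, 70 and 20 retrospective patients from 5, 3 and 7 sites in Finland, Sweden and Spain. With equal splits within country (assumed), m_w = (345²/5 + 70²/3 + 20²/7)/435 = 58.6. At ICC 0.01 to 0.05, DE is 1.58 to 3.88. The normal-approximation half-width at n = 435 goes from 4.7 to between 5.9 and 9.3 points.

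The effectiveness population will be smaller than 2,000, so the absolute half-widths in steps 3 to 5 are slightly optimistic.

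**The case against.** The strongest objection concerns the target of inference. Sites were chosen on purpose, not sampled. If the interval is meant only for the enrolled sites, the binomial variance is not anti-conservative and there is no error. That stands, and the point is limited accordingly. But the protocol's stated purpose is real-world practice, which reaches beyond those sites.

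Second, the size rests on an assumed ICC. At 0.05 the true site rates would have a standard deviation of 11 points, and nothing in the documents shows such a spread. At 0.005 the change from 2.2 to about 2.5 points hardly matters. This also stands: the direction is secure for a positive ICC, the amount is not.

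Third, the variation named in Protocol 6.3.1 is in the use of treatment modalities and settings across countries, not in conversion by site. It is weak evidence taken alone. The stronger support is how the endpoint handles early cardioversion, together with the German eligibility annex.

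Fourth, the 200-patient cap is there to stop any one site dominating, and no document says a site will reach it. Step 5 is therefore an illustration, not a forecast.

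A reader might also divide all 2,000 patients by the 33 active sites in Appendix I and find larger effects. The documents do not support that. The 33 belongs to enrolment of the last 810 patients, and its country rows add to 32. The whole-study figure is about 45.

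**Conclusion.** The point holds for the conversion rate in SAP 5.10 and Tables 15a-d. As an estimate for practice beyond the enrolled sites, the planned interval is too narrow under any non-trivial positive within-site correlation. With 45 equal sites and N = 2,000, the half-width would be about 2.5 points at ICC 0.005 and 2.7 to 4.0 at ICC 0.01 to 0.05, instead of 2.2. The design effect over the latter range is 1.4 to 3.2. Very unequal sites would make this worse. These sizes depend on the assumed ICC, which only the data can supply.

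A reader might infer that the HOI intervals need the same correction. The documents do not support that. The planning rates of 0% to 0.22% imply at most about 4 events per HOI in 2,000 episodes (0.0022 x 2,000 = 4.4), too few to estimate an ICC, so a design-effect-reduced HOI interval would have no usable input. A cluster of events at one site would also be visible, because the HOI and SAE listings carry a site column and every event has a narrative.

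Nor does any decision turn on the conversion interval. Conversion is secondary and descriptive, with no test, comparator or threshold, and the sample size was set on HOI precision. This is a worthwhile, inexpensive improvement, not a flaw in the primary analysis.

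**What to change.** In SAP 5.10 and the Table 15 shells, keep the exact interval and print beside it a 95% interval with site as the cluster, by Taylor linearisation or GEE with robust variance. Specify a small-sample correction where few sites contribute, as in the retrospective column (15 sites in the Appendix I projection, five of them supplying 345 of 435 patients). Report the number of contributing sites and the estimated design effect. Clustering on site also covers repeat episodes of a patient at the same site. Add one sentence saying which interval refers to the enrolled sites and which to wider practice.

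For the HOIs, keep Clopper-Pearson as planned and state the number of sites contributing events to each HOI. Do not add a design-effect-adjusted HOI interval.

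The cost is a few lines of SAP text, an extra row or column in the shells, and a standard SAS procedure. Site is already recorded, so no new data are needed. The only downside is a wider printed interval for conversion.

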5.1 Patient Disposition, Enrolment, and Demographics

5.1.1 Patient Disposition

NOTE: Patients may be enrolled in the study more than once in association with multiple treatment episodes of vernakalant IV. The study protocol does not prohibit multiple enrolments for a single patient. Patients receive a new, unique study ID at each new vernakalant treatment episode. **Note: the vernakalant treatment episode as referenced does not pertain to each infusion of vernakalant, as one treatment episode may involve multiple vernakalant infusions.** A summary of patients with multiple treatment episodes included in the analysis population set and the number of previous treatment episodes, if any, will be provided in the patient disposition table. All study tables and listings will treat each patient's subsequent administrations of vernakalant IV as occurring independently. For each patient with multiple treatment episodes, information regarding each episode including dates of informed consent, will be listed (**Listing 6**). Each patient's cumulative profile of SAEs (including HOIs) and contraindications by treatment episode will also be listed (**Listings 7-8**).

Patient disposition, per administration of vernakalant IV, will be summarised, as follows (**Table 2, Figure 1**):

- Total number of patients screened from site enrolment log (**Figure 1** only) and reasons for non-participation listed below, if available
 - No Informed Consent (Patient/Guardian unable to and/or refusal to give consent)
 - Patient not approached prior to vernakalant administration
 - Patient enrolled in an investigational drug or device clinical trial in the past 30 days prior to vernakalant administration
- Total number of patients enrolled in the registry
 - Total number of patients discontinued from the study due to conversion to sinus rhythm before vernakalant administration
- Total number of patients in the analysis population. All enrolled patients who meet the eligibility criteria and sign the informed consent form and are administered vernakalant IV are included in the analysis population. Patients discontinued from the study due to conversion to sinus rhythm before vernakalant administration or, based on patient request or ethic committee requirements, withdrawal of patient consent, will not be included in the analysis set.

- Total number of patients with single and multiple vernakalant treatment episodes in the analysis population
- For patients with multiple treatment episodes of vernakalant IV, number of previous treatment episodes
- Total number of patients who completed the study and reasons for discontinuation.
Note: For the interim analyses, patients displayed as “not complete” will include patients who do not have a complete End of Study case report form at the time of data extraction for the interim report.
- Number of patients excluded from analysis population either due to spontaneous conversion to sinus rhythm or withdrawal of patient consent

